1.6.3 Assessment of Potential Risks and Benefits

This clinical drug trial and its associated testing will be associated with some risks which we will try to minimize as outlined below:

-To minimize the risk for gastrointestinal disturbance, liraglutide dosing will be gradually increased over a 5-week period to achieve a maximum dose of 3.0 mg daily. Participants who experience mild to moderate gastrointestinal symptoms will contact the study team and the dose of liraglutide will be decreased and maintained at maximum tolerated dose until completion of the study. Participants who experience severe and/or recurrent gastrointestinal symptoms including acute gallbladder disease will be withdrawn from the study.

Abbreviated Title: Liraglutide in Teens Post-SG

Version Date: 1/30/23

-To minimize the risk for hypoglycemia for participants taking liraglutide, we will exclude patients on insulin or sulfonylurea therapy.

-To minimize the risk of pancreatitis in this study from liraglutide treatment, we will exclude patients with prior history of more than two episodes of pancreatitis as it may put them at higher risk for pancreatitis. If pancreatitis is clinically suspected (either based on signs/symptoms consisting of moderate to severe abdominal pain with nausea or vomiting) the following will take place: 1) Patient will be directed to local emergency department where amylase and lipase levels will be drawn 2) Abdominal ultrasound will be obtained. If a diagnosis of pancreatitis is likely or confirmed based on labs and/or imaging, the following additional actions will be taken. 1) The patient will be recommended for admission for further management or discharged home with supportive care depending on clinical severity. 2) Appropriate treatment will be initiated by primary medical team (usually, NPO and pain medications) if admitted. 3) The patient will be withdrawn from the study. 4) The IRB will be notified per guidelines for serious adverse effects.

-To minimize the risk of kidney failure in this study from liraglutide treatment, we will exclude patients with chronic kidney disease (eGFR <60; eGFR calculated using CKD-EPI equation).

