1.17.2.3 Dose Modifications

If intolerable symptoms persist after 3 days at any dose, the liraglutide dosage will be decreased by 0.6 mg daily. If the highest tolerable liraglutide dose is less than 0.6 mg daily, the study drug will be discontinued, but the participant will be asked to return for Study Visit 5.

If gastrointestinal symptoms resolve, then at the discretion of the PI, the dose of liraglutide may be increased after 3 days to the previous dose. If participant redevelops GI symptoms on previous dose, then they should continue the max tolerated dose for the remainder of the study.

Abbreviated Title: Liraglutide in Teens Post-SG

Version Date: 1/30/23

If a dose of liraglutide is missed, the study participants will be asked to resume the once daily regimen as prescribed with the next scheduled dose. They will be instructed not to administer an extra dose or increase the dose to make up for the missed dose.

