1.22 DISCONTINUATION OF STUDY INTERVENTION

Discontinuation from liraglutide does not mean discontinuation from the study, and remaining study procedures should be completed as indicated by the study protocol. If a clinically significant finding is identified after enrollment (including, but not limited to changes from baseline), the investigator or qualified designee will determine if any change in participant management is needed. Any new clinically relevant finding will be reported as an adverse event (AE).

Abbreviated Title: Liraglutide in Teens Post-SG

Version Date: 1/30/23

The data to be collected at the time of study intervention discontinuation will include the following:

- History and physical
- Bloodwork per investigator discretion
- The specific underlying reason for discontinuation of study intervention or participant discontinuation/withdrawal

Participants are free to withdraw from participation in the study intervention at any time upon request. Study medication can be discontinued abruptly without untoward effects from medication withdrawal.

An investigator may discontinue or withdraw a participant from the study for the following reasons:

- Completion of study intervention
- If any clinical adverse event (AE), laboratory abnormality, or other medical condition or situation occurs such that continued participation in the study would not be in the best interest of the participant
- Investigator discretion
- Positive pregnancy test or intention of becoming pregnant
- Participant unable to receive Liraglutide for 1 week or more
- Initiation of obesity or diabetes medications or obesity treatments not permitted during the trial

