1.32 POPULATIONS FOR ANALYSES

The following analysis populations will be evaluated and used for presentation and analysis of the data:

- **Screening Analysis** Dataset: All participants who have a signed informed consent form.
- **Intention-to-Treat (ITT) Analysis** Dataset: all treated participants. The ITT Population will consist of all adolescent subjects who were assigned to treatment regardless of whether the subject received treatment or not. A subject is considered assigned to treatment when the Investigator or Investigator's designee assigns a medication study number. For all analyses in the ITT Population, participants will be analyzed as treated, whether or not treatment was received.
- **Safety Analysis** Dataset: the subset of participants for whom safety analyses will be conducted: Participants who took at least one dose of study medication will be considered part of the Safety Analysis Dataset.

Abbreviated Title: Liraglutide in Teens Post-SG

Version Date: 1/30/23

- **Per Protocol Dataset:** Those who complied with the protocol sufficiently to ensure that these data would be likely to represent the effects of treatment according to the underlying scientific model (i.e., participants who took at least 80% of study intervention for 80% of the days within the treatment period).

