1.33.2 Analysis of the Primary Endpoint

The Primary Endpoint is estimation of required sample size for a later RCT through calculation of effect size for change in body mass index (BMI) from baseline to 16 weeks of liraglutide. The statistical hypothesis is: The data will be sufficient to calculate the effect size for change in BMI from baseline to 16 weeks for a 2-group experiment (placebo versus liraglutide). The primary outcome could be stated as the percentage of participants who are in the Per Protocol Dataset (who complied with the protocol sufficiently to ensure that these data would be likely to represent the effects of treatment according to the underlying scientific model (i.e., participants who took at least 80% of study intervention for 80% of the days within the treatment period). The study will be considered successful if more than 80% complete the trial.

The key variable that will be calculated is the effect size of the investigation. This value will be determined using the observed mean change in BMI from baseline to 16 weeks and the standard deviation for mean change observed with liraglutide treatment. The effect size (in this case, the Standardized Mean Difference (SMD) between two groups) will be calculated using Gpower 3.1.9.2 [90, 91] assuming the same standard deviation for both liraglutide-treated and control groups, a similar sample size for each group, and the observed difference in BMI from baseline to 16 weeks as the outcome of interest. Cohen's $d = (M_1 - M_2)/SD_{pooled}$. A plot will be created showing a range of sample sizes required for a between-groups t-test. For example, if we use the data from a recent randomized, double-blind, placebo-controlled phase 3 trial of liraglutide for adolescents who had not previously undergone bariatric surgery but had obesity [32], the liraglutide reduced BMI by -1.39 kg/m^2 ($SE=0.31$, $n=125$ over 1 year of treatment and the placebo group increased BMI by 0.19 kg/m^2 ($SE=0.33$, $n=126$) over the sample interval. If we found a similar reduction in BMI in adolescents who have obesity after bariatric surgery, the estimated effect size $d=0.4566$ (a difference of 1.58 kg/m^2 between groups with $SD 3.46$), a total sample size of 120 (60 per group) would be needed for one-sided $\alpha=0.05$ and power of 0.80 (Table 1).

[figure not shown]

Table 1, drawn using data obtained using G-Power 3.1.9.2 [90, 91]

Abbreviated Title: Liraglutide in Teens Post-SG

Version Date: 1/30/23

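### Sections 1.6.3 and 1.17.2.3 give opposite instructions for non-severe recurrent gastrointestinal symptoms, and the undefined 80% completion criterion inherits the conflict

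*Combined protocol and SAP*

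**What the plan says.** Two sections of the protocol tell staff what to do about gastrointestinal symptoms on liraglutide.

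- **Section 1.6.3** (Assessment of Potential Risks and Benefits). After mild to moderate symptoms, "the dose of liraglutide will be decreased and maintained at maximum tolerated dose until completion of the study". For worse or repeated symptoms: "Participants who experience severe and/or recurrent gastrointestinal symptoms including acute gallbladder disease will be withdrawn from the study".
- **Section 1.17.2.3** (Dose Modifications). If symptoms resolve then, at the principal investigator's discretion, "the dose of liraglutide may be increased after 3 days to the previous dose". If they come back: "If participant redevelops GI symptoms on previous dose, then they should continue the max tolerated dose for the remainder of the study". A participant who cannot tolerate even the lowest dose stops drug but is asked back for Study Visit 5.

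Other sections bear on how such a participant is counted:

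- Section 1.22: "Discontinuation from liraglutide does not mean discontinuation from the study".
- Section 1.23 asks that participants being removed for adverse events still return at the scheduled time for Visit 5.
- Section 1.33.2: "The study will be considered successful if more than 80% complete the trial". The same paragraph adds: "The primary outcome could be stated as the percentage of participants who are in the Per Protocol Dataset".
- Section 1.32 defines that dataset as "participants who took at least 80% of study intervention for 80% of the days within the treatment period".
- Section 1.38 stops the study if, once 20 participants have had the chance to finish 16 weeks, fewer than half are per protocol.

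**The concern.** A participant whose symptoms settle, whose dose is raised again and whose symptoms return has recurrent symptoms in the ordinary sense. Section 1.6.3 joins severity and recurrence with *and/or*, so recurrence alone is enough for withdrawal. Section 1.17.2.3 keeps the same participant on drug to the end. Following either instruction breaches the other.

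Gastrointestinal symptoms are the most common expected side effect of the drug, so this is not a remote case. Three things are at stake:

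1. A safety instruction for adolescents is ambiguous.
2. Per-protocol membership, and with it the stopping rule at 20 participants, depends on which section is followed.
3. The count toward the 80% criterion depends on it too. That count is further blurred because completing the trial is not defined and stands beside a per-protocol version of the outcome.

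**Working it through.** **The rules side by side**

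| Situation | Section 1.6.3 | Section 1.17.2.3 | Compatible? |
|---|---|---|---|
| Non-severe symptoms that recur | Withdrawn from the study | Stays on highest tolerated dose to the end | No |
| Symptoms that resolve | Dose lowered, then kept at the highest tolerated level | Dose may go back up, at discretion | Can be read together |
| Severe symptoms | Withdrawn from the study | Severity grade not mentioned | Section 1.38 has a separate grade 3 rule |

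Only the first row is a direct contradiction.

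**The plan's own figures (section 1.31)**

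- SD = 0.31 × √125 = 3.47 (stated 3.46). Standardized change = 1.39 / 3.46 = 0.4017. A one-sided paired t-test at 0.05 with n = 40 has power 0.803. The stated 80% is reproduced.
- Retention = 119/125 = 95.2%, a loss of 4.8%. 43 × 0.952 = 40.9, consistent with treating 43 to obtain 40.

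These figures are sound and are not at issue.

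**Margin in the 80% criterion**

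- With 43 treated: 35/43 = 81.4% passes and 34/43 = 79.1% fails. At least 35 completers are needed, so at most 8 can be lost.
- Background loss: 43 × 0.048 = 2.1, about 2 people. The ninth loss changes the verdict, and 9 − 2 = 7 withdrawals for recurrence.
- 7/43 = 16% of those treated. Section 1.6.1 cites gastrointestinal side effects in 64.8% of treated adolescents in the phase 3 trial. 0.648 × 43 = 27.9, and 7/27.9 = 25% of those expected to have any such event.
- If only 40 are treated, 32/40 = 80.0% is not more than 80%, so 33 are needed.

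**Chance of meeting the criterion**

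Let e be the share of treated participants withdrawn for recurrence. The documents give no value, so e is an assumption shown over a range. Treating participants as independent, each completes with probability p = 0.952 × (1 − e), and the number completing is binomial.

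| e | p | P(at least 35 of 43) | P(at least 33 of 40) |
|---|---|---|---|
| 0 (recurrent cases stay) | 0.952 | 0.9998 | 0.9995 |
| 5% | 0.904 | 0.98 | 0.97 |
| 10% | 0.857 | 0.85 | 0.79 |
| 15% | 0.809 | 0.56 | 0.50 |
| 20% | 0.762 | 0.27 | 0.23 |

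The table counts a withdrawn participant as a non-completer. If attending Visit 5 counts as completing, the effect shrinks, and section 1.33.2 does not say which applies.

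**Stopping rule at 20**

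10/20 is exactly half, so the rule fires at 9 or fewer per protocol, that is, with 11 or more outside the dataset. It is exposed to the same ambiguity but has a much wider margin.

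**The case against.** There are four fair objections.

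**The rules for resolved symptoms may not conflict.** A reader might infer a second contradiction, between holding the lowered dose and allowing it to rise again. The text does not force this. Section 1.6.3 speaks of the maximum tolerated dose, and the discretionary increase in section 1.17.2.3 can be read as the way that dose is found. This objection stands; the wording should be aligned, but it is not a second contradiction.

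**The size has no firm basis.** A reader might infer from the 64.8% figure that the criterion is likely to fail. That figure counts any gastrointestinal side effect over the treatment period of a trial that reported at 56 weeks, not recurrence within 16 weeks. The same trial had 10.4% discontinuing for adverse events. At that rate 0.104 × 43 = 4.5, so at most about 5 leave, and 38/43 = 88% passes. The documents do not describe that trial's handling of recurrence, so 10.4% does not bound a mandatory withdrawal rule, but it argues against presuming a high rate. The background 4.8% may also already include some losses for such symptoms. The objection stands as a limit on the claim.

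**Week-16 data need not be lost.** A reader might infer that withdrawn participants drop out of the BMI analyses. Sections 1.17.2.3, 1.22 and 1.23 already bring many of them back for Visit 5, and the key secondary analyses in section 1.33.3 use the intention-to-treat dataset with last observation carried forward. This stands too, although the rule applied still decides whether that BMI is measured on drug or off it.

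**The 80% problem is partly a separate defect.** Completion is undefined whatever the symptom rule says. That is correct, and the fix has to cover both.

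None of this removes the conflict over non-severe recurrence.

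**Conclusion.** The contradiction between sections 1.6.3 and 1.17.2.3 for non-severe recurrent symptoms is real, lies in current text and has no precedence rule to resolve it. It should be corrected whether or not it ever alters the success verdict, because staff cannot comply with both instructions.

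Its effect on the 80% criterion is conditional. With 43 treated and 4.8% background loss, about 7 withdrawals for recurrence would turn success into failure. The chance of success is 0.98 if 5% of treated participants are withdrawn for recurrence, 0.85 at 10%, 0.56 at 15% and 0.27 at 20%, against 0.9998 if they stay. Below about 5% the verdict would rarely change. These figures rest on an assumed recurrence rate, on independence between participants, and on counting withdrawn participants as non-completers.

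The documents do not support saying that the criterion will flip, that the power calculation is wrong, or that the week-16 BMI is lost.

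**What to change.** 1. Reconcile sections 1.6.3 and 1.17.2.3 into one rule for recurrent gastrointestinal symptoms, and define recurrence. Align the wording on resolved symptoms in the same edit. Which rule is kept is a clinical decision for the investigators.
2. State the rule once, refer to it from the other section, and check it against sections 1.22, 1.23 and 1.38 so that stopping drug and leaving the study are kept apart throughout.
3. In section 1.33.2, define completing the trial, name the denominator, and say how three groups are counted: those on a reduced dose, those who stop drug but attend Visit 5, and those withdrawn who attend Visit 5. State whether the 80% criterion refers to completion or to per-protocol membership.
4. In section 1.32, say whether the share of study intervention taken is measured against the target dose or the dose prescribed to that participant, since this decides whether someone kept on a reduced dose is per protocol.

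The cost is protocol wording and the amendment that carries it. The sample size, visits and data collected do not change.

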1.7 OVERALL DESIGN

This trial will be a multi-site open-label Phase II non-randomized pilot study involving two US sites: NIH Clinical Center and CNH. [name] and [name] at CNH will be involved in identifying and recruiting potential participants. They will be involved in answering questions about the study from interested patients but will not be screening or obtaining consent from participants. They will also be analyzing identifiable information from participants. All study visits will be conducted at a single site (NIH Clinical Center) to investigate the efficacy of liraglutide, a glucagon-like peptide-1 (GLP1) analogue to promote weight loss in pediatric patients (age 12 to <21y) who continue to have obesity (BMI ≥ 30 kg/m² or BMI $\geq 95^{\text{th}}$ percentile for age and sex) 1 year or more after vertical sleeve gastrectomy (SG) over 16 weeks.

Participants will undergo a telephone screening, followed by a screening visit to assess eligibility. Those found eligible will undergo a baseline evaluation to assess their glucose tolerance, lipids, levels of plasma GI hormones, appetite, body composition, energy intake, free living physical activity (by accelerometry), questionnaire measures, including assessment of weight related quality of life, mood, suicidality, and self-perception of body image. The trial will be divided into two consecutive periods. Period 1 will consist of 5 weeks of dose titration with goal of reaching max dose of 3 mg liraglutide daily with visits every 4 weeks over 16 weeks (including the 5 weeks of titration). The treatment period will then be followed by a 12-week period off study drug ending at week 28.

The primary outcome (change in BMI) will be statistically analyzed after participants have been treated with 3.0 mg daily liraglutide or max tolerated dose at 16 weeks. Secondary outcomes will also be measured at 16 weeks. BMI will be reassessed at follow-up at 28 weeks. There will be no interim analyses. Randomization will be stratified by birth sex assignment (Male versus Female), race (Non-Hispanic Black versus Other), and degree of weight loss after SG (those with typical post-SG weight loss, defined as $\geq 20\%$ BMI reduction versus those with poor post-surgical weight loss response, defined as $< 20\%$ BMI reduction post-SG), since expectation of benefit might differ in those unable to lose weight with SG.

1.8 SCIENTIFIC RATIONALE FOR STUDY DESIGN

We propose a pilot open-label treatment study to estimate effect sizes and identify potential responders for a subsequent larger randomized, double-blind, placebo-controlled trial. Data will be compared for patients with poor weight loss response to SG ($< 20\%$ BMI reduction) vs. those with typical post-SG weight loss ($> 20\%$ BMI reduction) but who have persistent obesity (BMI ≥ 30 kg/m² or $\geq 95^{\text{th}}$ percentile for age and sex) 1 year or more after SG. These data will allow determination of the sample size for a future fully powered randomized controlled trial.

1.9 JUSTIFICATION FOR DOSE

Eligible patients will be treated with daily subcutaneous liraglutide (starting at 0.6 mg daily with weekly dose escalations up to 3.0 mg per day or max tolerated dose). This dose is in line with liraglutide's treatment dose for adults with a BMI ≥ 30 kg/m² or BMI ≥ 27 kg/m² with at least one weight-related comorbidity (dose 3 mg daily).

Abbreviated Title: Liraglutide in Teens Post-SG

Version Date: 1/30/23

In addition, a recent randomized, double-blind, placebo-controlled phase 3 trial of liraglutide for adolescents (age 12 to <18 years) with obesity (BMI ≥ 30 kg/m² and $\geq 95^{\text{th}}$ percentile for age and sex) used a treatment dose of 3.0 mg daily [32] and had a comparable safety and tolerability profile to trials in adults with obesity with no new safety issues [49].

STUDY POPULATION

Adolescents are selected as the study subjects because of the dearth of relevant data for adolescents who have undergone SG. All races and ethnicities will be included. Since obesity is identified in large percentages among minority groups including Asian Americans, African American and Hispanic Americans, we anticipate good representation of all major races/ethnicities. It is expected, given our recruitment procedures targeting individuals living in the greater metropolitan Washington, D.C. area, that we will recruit rates of minority participation in excess of their representation in the Washington, D.C. metropolitan area: 64.2% Caucasian, 27.2% African American and 8.6% Hispanic.

Total number of subjects to be studied in the protocol: 50 maximum

Planned number of subjects to be screened in person: 50 maximum

Planned number of subjects to be treated with liraglutide: 43 maximum

Subjects will not be replaced if they withdraw or become ineligible.

1.10 INCLUSION CRITERIA

In order to be eligible to participate in this study, an individual must meet all of the following criteria:

1. Male or female, 12-20.999 years at screening visit
2. 12 months or more status-post vertical sleeve gastrectomy with a maximum of 10 years after surgery
3. BMI 30 kg/m² or $\geq 95^{\text{th}}$ percentile for age and sex
4. In good general health as evidenced by medical history
5. Ability to take subcutaneous medication and be willing to adhere to the daily subcutaneous liraglutide regimen
6. Ability to provide consent/assent before any trial-related activities as required per protocol
7. Stated availability for the duration of the study

1.11 EXCLUSION CRITERIA

An individual who meets any of the following criteria will be excluded from participation in this study:

Abbreviated Title: Liraglutide in Teens Post-SG

Version Date: 1/30/23

1. Current or recent (within 3 months of start of study drug initiation) use of weight loss medications such as phentermine, topiramate, lisdexamfetamine (prescribed specifically for weight loss; when prescribed for ADHD and dose is stable for last 3 months this medication will be allowed), orlistat, and naltrexone HCl/bupropion HCl, or liraglutide
2. Weight of more than 450 lbs. (because Dual-Energy X-ray Absorptiometry (DXA) scanning cannot be done in those exceeding this weight)
3. Current use of insulin or sulfonylurea or other medication affecting insulin secretion or GLP1 clearance such as a DPPIV inhibitor
4. Weight loss of more than 3% of body weight in the past 2 months
5. Current pregnancy, desire to become pregnant within study period, current lactation or, if sexually active, not willing to use adequate contraceptive measures
6. History of recurrent pancreatitis (greater than 2 episodes)
7. History of chronic kidney disease (eGFR <60)
8. History of gastroparesis
9. Personal or family history of medullary thyroid carcinoma or multiple endocrine neoplasia syndrome type 2
10. History of prior metabolic and bariatric surgery other than vertical sleeve gastrectomy
11. Current or prior use of any GLP-1 agonist medication during the 6 months before screening, including liraglutide.
12. Known or suspected allergy to trial medication, excipients, or related products
13. Treatment with another investigational drug or other experimental intervention within 3 months prior to enrollment in this trial
14. Individuals who have current substance abuse or a DSM 5 Axis I psychiatric disorder or DSM Axis II Mental Retardation diagnosis that in the opinion of the investigators would impede competence, compliance, or participation in the study
15. Suicidal ideation type 4 or 5, history of past suicide attempt, and suicidal behavior in the past month
16. Presence of a major medical illness not listed above

